Prior to rescue medication being administered, subjects will complete Day 119 study assessments, if possible. After confirming with the investigator that it is acceptable to take rescue medication, if a subject cannot return to the study site for assessments they will be instructed to complete a VASPI score on the remote monitoring device immediately prior to taking oral rescue medication. If the subject can return to the site, rescue may be performed by either oral or IV medication being administered or by increasing the pump speed to achieve a therapeutic dose of hydromorphone hydrochloride, or both.

Subjects who are treatment failures or those who are dropped from the study prior to randomization under this protocol will be permitted to enroll into Mallinckrodt clinical study CNS-HYD202US if the PI believes that the subject meets the study selection criteria and would benefit from participation in the study. For any subject continuing therapy on the CNS-HYD202US trial, the Day 119 (or failure visit) assessments will be considered the last day on the CNS-HYD201US trial and the first day of CNS-HYD202US. Subjects in the CNS-HYD201US trial who were dropped prior to randomization and judged by the primary physician to benefit from participation in CNS-HYD202US will complete the study visit that they are on, go directly into CNS-HYD202US and complete scales there at the Screening and Baseline Visit. Subsequent visits, including re-titration onto hydromorphone hydrochloride if necessary, will be considered part of the CNS-HYD202 US trial.

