#### 9.7 Final Visit

Subjects who do not enter the CNS-HYD202US long-term safety trial will return to the investigational site for the final visit 2 weeks ( $\pm$  4 days) after discontinuation from the trial. At the final study visit subjects will be assessed for AEs and clinical signs or symptoms of an inflammatory granuloma as well as other procedures according to Appendix A, Table A- 2. Also during the final visit the investigator will remove all study drug from the subjects pump and will continue the subjects normal standard of care.

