#### 14.0 STATISTICAL CONSIDERATIONS

# 14.1 Sample Size Determination

Approximately 150 subjects will be enrolled at up to thirty (30) US investigative sites to obtain approximately 80 subjects who qualify for randomization into the double-blind period on Day 84. This enrollment is based on a combined drop out and treatment failure (ie, > 50 mm on a 100 mm VASPI score for the last 5 days with non-missing data prior to the double-blind period) rate of approximately 45%.

During the double-blind period, the true treatment failure rate in the hydromorphone hydrochloride arm is assumed to be at most 20%. Based on a two-sided, two-sample comparison

of proportions at the alpha = 0.05 level of significance, a sample size of 80 subjects (40 per arm) will provide greater than 90% power to detect an increase in the treatment failure rate of 35% (ie, the control group who will have their dose titrated downward has a failure rate of 55%).

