j. COWS, SOWS, BPI, SF-MPQ and PGIC will be conducted at each office visit as specified in the Schedule of Events. Assessments conducted per the Schedule of events should be completed prior to any dose adjustment or providing any oral supplemental opioid medication for withdrawal symptoms or rescue, if possible

5 Data Management

Data management, including database design, development of the data dictionary, and coding of adverse events and medications will be performed at Social and Scientific Services (S-3), the CRO managing data base entry and cleaning. Data will be entered into electronic case report forms (eCRFs) at the study sites. Logic and consistency checks will be performed on all data entered into the eCRFs to ensure accuracy and completeness. Refer to the Data Management Plan for further details. An ePRO device will also be used to collect VASPI measurements from Day 77 to 119.

A paper CRF page will be used by the Unblinded Pump Operator to record dose administration information during Days 84 to 119. The protocol indicates that this CRF page will be held at the site and collected after the subject has completed the trial for manual entry into the database. The actual practice being followed is that the unblinded site representative sends this CRF page to the unblinded Clinical Research Associate for monitoring. These CRFs will be collected at the end of the study and sent in for manual entry into the database.

6 Definition of Populations

The intent-to-treat (ITT) population includes all subjects who are randomized on Day 84 to either the active or control group in the Double-Blind Randomized Withdrawal portion of this study and receive at least one day of hydromorphone hydrochloride intrathecal treatment during the randomization period. All efficacy analyses will be carried out using the ITT population. In all efficacy analyses, subjects will be included in the group based on the group to which they were randomized.

The Safety population includes all subjects who have study medication loaded into their intrathecal pump (i.e. any exposure to study medication). Safety analyses will be carried out using the Safety population. In all safety analyses, subjects will be included in the group based on the treatment they received (i.e., randomized withdrawal or same dose hydromorphone continuation). Subjects who do not reach the point of randomization will be included in the overall column only.

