8.6 Comments on Statistical Analysis

The following general comments apply to all statistical analyses and data presentations:

Summaries will include frequency and percentages for categorical data and frequency, mean, standard deviation, median, minimum, and maximum for quantitative data.

- Where appropriate and unless otherwise specified, analyses will be presented by randomized treatment arm: hydromorphone arm or titrated down (control) arm.
- Duration variables will be calculated using the general formula: Duration = (end date start date) + 1.
- Individual subject listings of all data represented on the eCRFs will be provided to facilitate the investigation of tabulated values and to allow for the clinical review of all data.
- Version 9.1 or greater of SAS statistical software package will be used to provide all summaries, listings, and graphs described in this document.
- All raw data will be presented to the original number of data places. The means and medians will be presented to one more decimal place than the raw data. The standard deviations will be presented to two more decimal places than the raw data. For averages of averages, the means and medians will also be presented to one more decimal place than the raw data and the standard deviations will also be presented to two more decimal places than the raw data.
- Generally, the denominator for percentages will be based on the number of subjects in the study population. However, for cases where appropriate, the denominator for percentages will be based on the number of subjects with non-missing data appropriate for summary purposes. Unless otherwise noted, all percentages will be presented to one decimal place.
- There are approximately 10-30 study sites in this study. Due to the large number of study sites and the small numbers of subjects per site, the analysis of efficacy endpoints will not include adjustments for study site. However, descriptive summaries of the primary endpoint will be provided by site.

• Analyses for the randomization phase, Day 84 through Day 119, will be calculated for the period defined as randomization date through end of study date, as study day of randomization and Day 119 visit may not always occur on the scheduled study days (84 and 119) due to various circumstances.

9 Statistical Analyses

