9.6.1 Adverse Events

Unless otherwise noted, analyses will be based on treatment-emergent adverse events (TEAEs), defined as those events that begin or worsen in severity after the first treatment with study drug at Baseline. For AEs with missing start dates, the AE will be considered treatment-emergent unless there is additional information indicating that the AE started prior to the first study drug treatment.

Adverse events will be coded to system organ class and preferred term using MedDRA; the dictionary version will be noted in the CSR. AE severity will be assessed and summarized using the Common Terminology Criteria for Adverse Events (CTCAE) v 4.03.

AE incidence tables will include the number and percentage of subject reporting at least one AE, as well as, the number and percentage of AEs summarized by MedDRA system organ class and preferred term. Subjects with two or more AEs in the same system organ class will be counted once for that system organ class; likewise for preferred term. For 'by severity' and 'by relationship to study treatment' tables, subjects will be counted once at the maximum severity and at the strongest causal relationship, respectively. Summaries of treatmentrelated AEs will include those events classified by the investigator as having a possible or probable relationship to study drug (or unknown relationship). Tables will be produced for the following: TEAEs, treatment-related TEAEs, TEAEs by strongest relationship, TEAEs by maximum severity, treatment-emergent serious adverse events (TESAEs), TESAEs by strongest relationship, treatment-related SAEs, and TESAEs by maximum severity. An overall AE summary table will provide top level subject counts for all the AE analyses noted. In addition, the AE summary table will include the number and percentage of subjects reporting any AE (including non TEAEs), the number and percentage of subjects with an AE that led to withdraw of study drug, and the number and percentage of subjects with an AE with outcome of death.

Complete listings of all AEs will be provided (non TEAEs will be flagged with a '*'). In addition, data listings of all SAEs, AEs leading to discontinuation, and AEs leading to death will also be provided.

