Appendix A

The following Tables, Listings and Figures are anticipated to be produced to display the results of the statistical analyses. Additions or deletions to this list may be made in order to produce the analyses described in this SAP.

Number	Title	Analysis
		Population
	Tables	
14.1.1	Subject Disposition	All Enrolled Subjects
14.1.2	Analysis Populations	All Enrolled Subjects
14.1.3	Demographics and Baseline Characteristics	All Enrolled Subjects
14.1.4	Medical History	All Enrolled Subjects
14.1.5.1	Prior Medications	All Enrolled Subjects
14.1.5.2	Concomitant Medications	All Enrolled Subjects
14.1.6	12-Lead Electrocardiogram	All Enrolled Subjects
14.2.1.1.1	Treatment Failure Rate	ITT
14.2.1.1.2	Treatment Failure Rate	ITT Excluding Site 028
14.2.1.2	Treatment Failure Rate by Site	ITT
14.2.2.1	Time to Rescue after Randomization	ITT
14.2.2.2	Time to Rescue after Randomization	ITT Excluding Site 028
14.2.3.1.1	Pain Indicators Summary	ITT
14.2.3.1.2	Pain Indicators Summary	ITT Excluding Site 028
14.2.3.1.3	Oral Opioid Supplement Consumption	ITT
14.2.3.1.4	Oral Opioid Supplement Consumption	ITT Excluding Site 028
14.2.3.1.5	Patient Global Impression of Change Summary	ITT
14.2.3.1.6	Patient Global Impression of Change Summary	ITT Excluding Site 028
14.2.3.2.1	Brief Pain Inventory - Pain Severity Measures	ITT
14.2.3.2.2	Brief Pain Inventory - Pain Severity Measures	ITT Excluding Site 028
14.2.3.3.1	Brief Pain Inventory - Pain Interference	ITT
14.2.3.3.2	Brief Pain Inventory - Pain Interference	ITT Excluding Site 028
14.2.3.4.1	Patient Global Impression of Change (PGIC)	ITT
14.2.3.4.2	Patient Global Impression of Change (PGIC)	ITT Excluding Site 028
14.2.3.5.1	Short-form McGill Pain Questionnaire (SF-MPQ)	ITT
14.2.3.5.2	Short-form McGill Pain Questionnaire (SF-MPQ)	ITT Excluding Site 028
14.2.3.6.1	Visual Analog Scale of Pain Intensity (VASPI)	ITT
14.2.3.6.2	Visual Analog Scale of Pain Intensity (VASPI)	ITT Excluding Site 028
14.3.1.1.1	Overview of Adverse Events - Open Label Phase	Safety
14.3.1.1.2	Overview of Adverse Events - Randomized Phase	Safety

14.3.1.1.3	Overview of Adverse Events - Overall	Safety
14.3.1.2.1	Incidence of Adverse Events by System Organ Class	Safety
	and Preferred Term - Open Label Phase	
14.3.1.2.2	Incidence of Adverse Events by System Organ Class	Safety
	and Preferred Term - Randomized Phase	
14.3.1.2.3	Incidence of Adverse Events by System Organ Class	Safety
	and Preferred Term - Overall	

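### Randomized-phase adverse event percentages take no account of time at risk, which the plan's own failure assumptions make shorter in the control arm

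*SAP*

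**What the plan says.** SAP 9.6.1 sets the AE measure: "AE incidence tables will include the number and percentage of subject reporting at least one AE". Under SAP 8.6 the denominator is a head count: "Generally, the denominator for percentages will be based on the number of subjects in the study population". SAP Appendix A lists separate tables for this phase, starting with "Overview of Adverse Events - Randomized Phase" (14.3.1.1.2), all on the Safety population. SAP section 6 fixes the grouping: "subjects will be included in the group based on the treatment they received (i.e., randomized withdrawal or same dose hydromorphone continuation").

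Three provisions govern how long a subject is observed after randomization:

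- SAP 8.6: randomized-phase analyses "will be calculated for the period defined as randomization date through end of study date", so the window differs between subjects.
- Protocol 3.1, for subjects who continue into CNS-HYD202US: "the Day 119 (or failure visit) assessments will be considered the last day on the CNS-HYD201US trial".
- Protocol 9.7, for the rest: "Subjects who do not enter the CNS-HYD202US long-term safety trial will return to the investigational site for the final visit 2 weeks" after discontinuation, with a margin of 4 days either way.

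On how many subjects fail, Protocol 14.1 and SAP 8.1 assume at most 20% in the maintained arm, while "the control group who will have their dose titrated downward has a failure rate of 55" per cent. Protocol 1.4 expects most tapered subjects to fail before the near-zero dose step.

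Neither document plans a person-time AE rate, a time-to-first-AE analysis or a common observation window. Table 14.3.6.2 summarizes randomized-phase drug exposure but is not tied to the AE tables.

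**The concern.** A percentage of subjects with at least one event depends on how often events occur and on how long subjects are watched. Here the second factor is linked to the efficacy outcome: the arm with more failures is watched for less time. Two arms with the same AE rate would then show different percentages.

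SAP 7.2 and 9.5.2 call safety the most important secondary endpoint, and SAP 9.6 addresses it primarily through AE incidence and severity and granuloma rates. Even without a between-arm test, the columns will be read against each other. The SAP already deals with unequal follow-up for time to rescue (Kaplan-Meier with censoring, SAP 9.5.2) but has no counterpart for AEs.

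**Working it through.** **Plan's own figure.** The failure rates come from the sample size statement, so I checked that first. With 40 per arm, 20% against 55% and two-sided alpha 0.05, the pooled rate is 0.375. The null standard error is √(2 × 0.375 × 0.625 / 40) = 0.108 and the alternative is √((0.20 × 0.80 + 0.55 × 0.45) / 40) = 0.101. Power = Φ((0.35 − 1.96 × 0.108) / 0.101) = 0.914. Exact enumeration of the Pearson test gives 0.915. The claim of more than 90% reproduces.

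**Inputs from the documents.** Period T = 35 days (Day 84 to Day 119). Failure proportion f = 0.20 (maintained) and 0.55 (control).

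**Assumptions not in the documents.** The AE hazard h is constant and equal in both arms. The failure-time distribution is the same in both arms. Observation ends at failure. The 35-day AE risk is 30%, giving h = −ln(0.70) / 35 = 0.0102 per day.

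**Mean time at risk** = (1 − f) × 35 + f × (mean failure day). For failures uniform over 0–35 days:

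- Maintained: 0.80 × 35 + 0.20 × 17.5 = 31.5 days
- Control: 0.45 × 35 + 0.55 × 17.5 = 25.4 days, a ratio of 0.81

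**Crude percentage** = (1 − f) × 0.30 + f × (average of 1 − exp(−ht) over failure times). For uniform exits that average is 1 − 0.30 / 0.3567 = 0.159.

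- Maintained: 0.80 × 0.30 + 0.20 × 0.159 = 27.2%
- Control: 0.45 × 0.30 + 0.55 × 0.159 = 22.2%

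The difference is 4.9 points before rounding and the crude ratio is 1.22, although the hazards are equal. A rate per subject-week would give a ratio of 1.00: in both arms h × 7 × 100 = 7.1 events per 100 subject-weeks.

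**Sensitivity to failure timing** (35-day risk 30%, differences computed before rounding). The last column is the control-to-maintained hazard ratio at which the two crude percentages become equal.

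| Failure days | Mean days, maintained / control | Crude %, maintained / control | Difference (points) | Crude ratio | Cancelling hazard ratio |
|---|---|---|---|---|---|
| 7–14 | 30.1 / 21.5 | 26.0 / 19.1 | 7.0 | 1.36 | 1.45 |
| 0–35 | 31.5 / 25.4 | 27.2 / 22.2 | 4.9 | 1.22 | 1.27 |
| 14–28 | 32.2 / 27.3 | 27.8 / 24.1 | 3.8 | 1.16 | 1.19 |
| 21–35 | 33.6 / 31.1 | 29.0 / 27.1 | 1.8 | 1.07 | 1.08 |
| 28–35 | 34.3 / 33.1 | 29.5 / 28.6 | 0.9 | 1.03 | 1.04 |

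The near-zero step falls on Day 112, day 28 of the period, so the last row fits Protocol 1.4's expectation for control least well. Over 35-day risks from 10% to 70%, the crude ratio runs from 1.02 to 1.39.

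**Effect of the final visit.** If every subject had the extra 14 days, the uniform case becomes 31.5 + 14 = 45.5 against 25.4 + 14 = 39.4 days, a ratio of 0.87. The gap narrows but remains.

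**The case against.** A reader might infer that the tables overstate risk on the maintained arm. The documents do not support that. Shorter control follow-up lowers the control percentage and leaves the maintained arm's own figure untouched; only the contrast moves. Even its net direction cannot be fixed, because the design anticipates withdrawal symptoms in the tapered arm: oral opioid is allowed for them, and the COWS and SOWS withdrawal scales are collected at each visit. With failures on days 21–35 or uniform, a control hazard only 1.08 to 1.27 times the maintained hazard cancels the follow-up effect. This limits the claim but does not remove the problem, since percentages alone cannot separate follow-up from hazard and could hide a real control excess.

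A reader might also take the failure visit as everyone's last day. Protocol 3.1 says so only for those continuing into CNS-HYD202US, and the roll-over share is not given. Nor do I find a passage requiring a subject who fails on the pain-score criterion to leave that day; Protocol 3.5.1.3 counts such a failure whether or not rescue is given. Both points reduce the expected gap.

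The shift is also modest against the noise. With 40 per arm, the standard error of the uniform-case difference is √(0.272 × 0.728 / 40 + 0.222 × 0.778 / 40) = 9.6 points, about twice the shift. The AE tables are descriptive, and the exposure summary and time-to-rescue curves would let a careful reader see the imbalance. That stands, but the reader would still have to reconstruct the adjustment.

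Finally, person-time rates assume a roughly constant hazard, while the control dose changes weekly, and exit for pain may itself be related to AEs. The first argues for adding a time-to-event display. The second is a limitation of any of these summaries.

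**Conclusion.** The point holds as a gap in reporting; no stated rule is in error. Randomized-phase AE percentages are not adjusted for time at risk, and the plan's failure assumptions make that time shorter in control, at least for failures who roll over. Under the stated assumptions, the follow-up component alone is about 5 points at 30% risk with uniform exits, and 0.9 to 7.0 points across the timings examined. The documents give no failure-time distribution, so the size cannot be pinned down further. The net sign of the crude contrast is unknown.

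A related gap affects any remedy. SAP 9.6.1 ties treatment emergence to first study drug and does not say how an event is assigned to the randomized phase. The protocol gives three end points for AE collection: the final visit (5.1), the end of study medication for non-serious events (13.1) and a follow-up telephone call (13.2.1).

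**What to change.** Keep the percentages and make these additions:

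- In Tables 14.3.1.1.2, 14.3.1.2.2 and 14.3.1.3.2, show by arm the subject-weeks from randomization to end of study and the number of events per 100 subject-weeks. Counting all events needs one denominator per arm; first-event rates would need a separate one for each preferred term.
- For the overview only, add Kaplan-Meier time to first AE and first SAE by arm, because the hazard may change as the control dose falls.
- State which events count as randomized-phase (onset or worsening on or after randomization, up to a defined last day), whether the 2-week final visit falls inside that window, and reconcile the three AE collection periods.
- Identify the addition in the CSR as made after unblinding, since SAP section 2 records that the study was already unblinded.

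Randomization, end-of-study and AE onset dates are already collected, so the locked database is not altered. The cost is slightly larger tables and one additional display. The rates rest on a roughly constant hazard, which a footnote should say.

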9.6.2 Vital Signs and Weight

Systolic and diastolic blood pressure (mmHg), radial pulse (beats/minute), breathing rate (breaths/minute), and temperature (°C) will be obtained at Baseline and each study visit. Weight (kg) will be collected at screening and each study visit.

All vital signs and weight measurements as well as change from Baseline for these measurements will be summarized by treatment arm at each visit. A listing of weight and vital signs will also be provided.

The number and percentage of subjects with potentially clinically significant vital signs will be summarized at each visit by vital sign and treatment arm. A listing of subjects with potentially clinically significant vital signs will also be presented. Table 3 contains the criteria for identifying potentially clinically significant vital sign values.

Table 3: Criteria for Identifying Potentially Clinically Significant Vital Sign Values

Vital Sign Parameter	Criteria				
Systolic Blood Pressure (mmHg)	>160 mmHg or increase of ≥20 mmHg from baseline				
Systolic Blood Pressure (mmHg)	<95 mmHg or decrease of ≥20 mmHg from baseline				
Diastolic Blood Pressure (mmHg)	>110 mmHg or increase of ≥15 mmHg from baseline				
Diastolic Blood Pressure (mmHg)	<50 mmHg or decrease of ≥15 mmHg from baseline				
Heart Rate (bpm*)	>100 bpm or increase of \geq 15 bpm from baseline				
Heart Rate (bpm*)	<50 bpm or decrease of ≥15 bpm from baseline				
Weight (kg) Gain	>10% weight increase				
Weight (kg) Loss	>10% weight decrease				

*bpm = Beats per minute

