## **Central Nervous System (CNS)**

The precise mode of analgesic action of opioid analgesics is unknown. However, specific CNS opiate receptors have been identified, and opioids are believed to express their pharmacological effects by combining with these receptors. Hydromorphone depresses the cough reflex by direct effect on the cough center in the medulla. Hydromorphone produces respiratory depression by direct effect on brain stem respiratory centers. The mechanism of respiratory depression also involves a reduction in the responsiveness of the brain stem respiratory centers to increases in carbon dioxide tension. Hydromorphone causes miosis. Pinpoint pupils are a common sign of

01 August 2016 21 CONFIDENTIAL

opioid overdose, but are not pathognomonic (e.g., pontine lesions of hemorrhagic or ischemic origin may produce similar findings). Marked mydriasis rather than miosis may be seen with hypoxia in the setting of Dilaudid Injection or Dilaudid-HP overdose.

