# 5.4 Vital Signs

Systolic and diastolic blood pressure, radial pulse, breathing rate, temperature, and weight will be obtained and recorded at screening, baseline (if a different visit) and each study visit.

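### SAP Table 3 has no breathing-rate criterion, so subjects with low breathing rates or large falls will not be counted, although the protocol names respiratory depression as an effect of the drug

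*SAP*

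**What the plan says.** Collection is clear in both documents. Protocol 5.4 states: "Systolic and diastolic blood pressure, radial pulse, breathing rate, temperature, and weight will be obtained and recorded at screening", and adds baseline and every study visit. In SAP 9.6.2, "breathing rate (breaths/minute), and temperature (°C) will be obtained at Baseline and each study visit".

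The same SAP section then sets out three kinds of output:

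- **Descriptive summaries.** "All vital signs and weight measurements as well as change from Baseline for these measurements will be summarized by treatment arm at each visit".
- **A full listing.** "A listing of weight and vital signs will also be provided".
- **A threshold-based screen.** "The number and percentage of subjects with potentially clinically significant vital signs will be summarized at each visit by vital sign and treatment arm". Those subjects are also to be listed. For the limits, "Table 3 contains the criteria for identifying potentially clinically significant vital sign values".

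Table 3 has a high and a low criterion each for systolic pressure, diastolic pressure and heart rate, and a gain and a loss criterion for weight. It has nothing for breathing rate or temperature, and the SAP gives no reason for leaving them out.

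On the drug's effects, the Central Nervous System part of Protocol 1.3.1 states: "Hydromorphone produces respiratory depression by direct effect on brain stem respiratory centers". Protocol 3.6.1 pairs respiratory depression with hypotension as effects attributed to combined use with other epidural drugs. Protocol 3.6.2 asks for the medical monitor to be consulted before a subject taking other drugs that may depress respiration is enrolled.

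**The concern.** Table 3 works as a closed list. A programmer following the SAP will apply its eight criteria and no others, so the tables of potentially clinically significant values will contain no breathing-rate line. A reader of those tables would see counts for low blood pressure, one of the two interaction effects named in Protocol 3.6.1, and no count for the sign of the other.

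Vital signs also carry more weight here than in many trials. Under Protocol 5.3, laboratory tests and ECGs are done only at screening, so vital signs are the main numeric safety measurements repeated during treatment. At stake is whether the safety report can say how many subjects in each arm, at each visit, had a breathing rate outside a stated limit or a large fall from baseline.

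**Working it through.** No sample size, rate or test enters this point, and the plan gives no figure to reproduce. The check sets what is collected beside what can be flagged. Table 3's heart rate is taken to be the radial pulse that is collected.

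**Step 1. Measures collected against Table 3 criteria**

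| Measure (Protocol 5.4, SAP 9.6.2) | Criterion in Table 3 |
|---|---|
| Systolic pressure | high and low |
| Diastolic pressure | high and low |
| Pulse | high and low |
| Weight | gain and loss |
| Breathing rate | none |
| Temperature | none |

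Four of 6 measures have criteria (4 × 2 = 8 criteria); 6 − 4 = 2 have none.

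**Step 2. What this does to the outputs.** Appendix A plans Table 14.3.5.2.1 (open-label phase) and Table 14.3.5.2.2 (randomized phase) for potentially clinically significant vital signs. Both depend on Table 3, as does the listing of flagged subjects. With no criterion, the number of breathing-rate values that can enter them is zero by construction.

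**Step 3. Where breathing rate does appear**

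- Tables 14.3.5.1.1 and 14.3.5.1.2 summarise values and changes from baseline. SAP 8.6 requires the minimum and maximum as well as the mean, standard deviation and median for quantitative data. The lowest value and the largest fall in each arm at each visit will therefore be printed.
- Listing 16.2.11 gives vital signs by subject.
- Protocol 5.1 requires abnormal vital-sign changes from baseline to be graded, assessed for causality and recorded, without reference to Table 3. Adverse events are asked about at each visit and tabulated under SAP 9.6.1.

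**Step 4. What none of these gives.** A minimum identifies one extreme per arm and visit. It does not say whether one subject or several were beyond a limit. The listing holds that information, but a reader would have to extract it by eye with no stated limit. Adverse event tables count reported events, not measured values. The count by arm and visit is the one item missing.

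**The case against.** The strongest reply is that little is lost. Breathing rate is measured, summarised with minima, listed in full and backed by a protocol duty to grade abnormal changes. SAP 9.6 places vital signs among the other safety assessments, behind adverse events and granuloma rates. Table 3 is a descriptive screen that feeds no inference, and the documents give no breathing-rate limit to adopt.

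Much of this stands, and it rules out four stronger readings that a reader might infer:

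- **That respiratory depression goes unscreened.** It does not: breathing rate is collected, summarised and listed, and respiratory events are captured as adverse events.
- **That only means are reported, so a single low value disappears.** One subject's fall does barely move a mean, but SAP 8.6 requires the minimum, so an argument from dilution of the mean fails.
- **That the safety conclusion rests on adverse event reporting alone.** The summaries and listing are separate routes.
- **That respiratory depression is the main hazard the documents name.** They name it several times, but the hazard given particular attention is catheter-tip granuloma (Protocol 3.2.2, SAP 7.2).

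The reply does not supply the missing count, nor explain why four measures have one and breathing rate does not. The adverse event route also has a loose end. The optional titration column of the visit schedule (Protocol Table A-1, SAP Table 1) marks vital signs but, as the table reads, not adverse event assessment, whereas Protocol 5.1 calls for it at each visit.

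**Conclusion.** The point holds as a gap in threshold-based flagging, not in collection or in reporting as a whole. Two of the 6 measures lack a criterion. For breathing rate this matters because the protocol names respiratory depression as a direct effect and an interaction risk. Temperature is noted for completeness.

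The effect is modest. No endpoint, analysis population or hypothesis test changes, and individual low values remain visible. What cannot be produced is a count or flagged listing of subjects with out-of-range breathing rates or large falls.

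The conclusion assumes that Table 3 is applied as written; nothing in SAP 9.6.2 suggests that further criteria would be added. Even with a breathing-rate row, the count would cover only readings taken at visits.

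**What to change.** Add a breathing-rate row to SAP Table 3 with a low-value limit and a fall-from-baseline limit. Carry it into Tables 14.3.5.2.1 and 14.3.5.2.2 and the listing of flagged subjects. For temperature, add a row or state why none is needed.

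The documents give no limits and none is proposed here. The sponsor's medical monitor should set them, without reference to arm-level breathing-rate data, and record the basis for the choice.

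SAP Section 2 reports database lock on 18 October 2017 and says that the study was already unblinded when the full analysis was resumed. A criterion added now is therefore post hoc and must be identified as such in the clinical study report, as SAP Sections 2 and 8.4 require for unplanned analyses. That is the small downside.

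The cost is one table row and a rerun of outputs already planned. The data are already collected and no change to the locked database is needed.
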